8.2 Outcome Measures

(Outcome Measures are for infants only; maternal data are to be used as covariates, not as outcomes)

8.21 Primary Endpoints for Cohorts 1 and 2

Toxicity Endpoints: Toxicity from study entry through 6 weeks of life

- Adverse events of Grade 3 or 4 severity or death (primary safety endpoint for final analysis)
- Suspected adverse drug reaction (SADR) of Grade 3 or 4 severity or death (primary safety endpoint for dose finding guidelines described in Section 8.52) but secondary safety endpoint for the analyses described in Section 8.71)

Pharmacokinetic Endpoints: (See Section 9.0: Clinical Pharmacology Plan)

8.22 Primary Response Variables for Cohorts 1 and 2 Pharmacokinetic parameters (See Section 9.0)

8.23 Secondary toxicity endpoints for Cohorts 1 and 2: Toxicity from study entry weeks through 24 weeks of age

- Adverse events of Grade 3 or 4 severity or death
- Suspected adverse drug reaction (SADR) of Grade 3 or 4 severity or death

8.24 Secondary Response Variables for Cohorts 1 and 2

- UGT1A1 genotype (presence or absence of *28/*28 genetic variant)
- SLCO1B3 (rs2117032-C/T) genotype
- Hyperbilirubinemia defined as total bilirubin exceeding 16.0 mg/dL or infant receiving phototherapy, or transfusion therapy, or other therapies for hyperbilirubinemia

8.3 Randomization and Stratification

There will be no randomization. The infant's RAL exposure in utero will be an accrual and an analysis stratification factor.

8.4 Sample Size and Accrual

Under Protocol Version 1.0, the study target enrollment was approximately 50 infants and their mothers in order to accrue minimum of 12 and 20 PK evaluable neonates in Cohorts 1 and 2, respectively. These sample sizes have been determined on the basis of data needed for the PK analysis. The team estimated it will take 4 years to accrue 32 evaluable participants.

To date, Cohort 1 RAL-naïve, Cohort 1 RAL-exposed, and Cohort 2 RAL-naïve groups were fully accrued under protocol Version 1.0. Cohort 2 RAL-exposed group will open to accrual under protocol Version 2.0 with a minimum accrual of 8 infants. The team estimates it will take 1 year to accrue 8 evaluable participants.

8.5 Monitoring and Safety Guidelines

The team will assess safety on routine monitoring conference calls which will occur at least every 4 weeks for Cohorts 1 and 2. Safety analyses will be performed at full accrual to Cohort 1, at interim analysis when 8 participants have been accrued to Cohort 2 and at full accrual to Cohort 2, evaluating whether the safety guidelines specified in Section 8.52 have been met. For dose finding purposes, infants who have been excluded from the PK analyses, due to evidence of problematic exposure to the study medication, will also be excluded from evaluation of the safety guidelines.

The attribution of relationship of serious adverse events to study drug for the purposes of employing the start, stop and pause rules will be by consensus among the site investigator, study team (which includes representatives from Merck) and DAIDS medical officer; if unanimous agreement between them cannot be established, the attribution made by the majority of these 3 persons or entities will be used. Gradation of relationship will use the following terminology: Not related, probably not related, possibly related, probably related or definitely related.

8.51 Monitoring of Safety Data by the Protocol Team and the Study Monitoring Committee (SMC)

Since Phase I studies are not routinely reviewed by a Data and Safety Monitoring Board (DSMB), it is the responsibility of the protocol team to interpret safety data, and make decisions regarding SADRs that are needed to protect participants from undue risk.

The safety and tolerability of the study agent will be monitored by means of adverse events reports and toxicity reports presenting laboratory and clinical events. It is required that the data required for the toxicity reports be entered into the database within 72 hours of the time at which the results of the laboratory tests or clinical examinations become available.

Reports compiled by the Data Management Center (DMC) will be reviewed and discussed by the Protocol Team on conference calls held at least every 4 weeks. Data on accrual, pharmacokinetics and toxicity will be reviewed.

In addition, an independent IMPAACT Study Monitoring Committee (SMC) will review this study regularly, following policies described in the IMPAACT Manual of Procedures. The composition of the SMC will include the SMC Chair; IMPAACT Chair or Vice Chair; IMPAACT Treatment Scientific Committee Chair or Vice Chair; representatives of the IMPAACT Operations Center, Statistical and Data Management Center, and Laboratory Center; and representatives of NIAID and NICHD.

SMC reviews will occur at least annually and on a more frequent or *ad hoc* basis if any safety issues or concerns arise. *Ad hoc* reviews may also be triggered by temporary suspension of accrual or pausing administration of study product due to safety concerns, as outlined in Section 8.52 below. Based on any of its reviews, the SMC may recommend that the study proceed as currently designed, proceed with design modifications, or be discontinued. The SMC may also provide operational recommendations to help address any study implementation challenges that may be identified during their reviews.

The SMC will monitor study progress (see Section 8.6), quality of study conduct, and participant safety. The SMC will generally review the same types of data reports as the Protocol Team. For *ad hoc* or triggered safety reviews, more limited data may be reviewed, focusing on the events that triggered the reviews.

8.52 Guidelines for the Evaluation of Safety Data (See Section 9.0 for Pharmacokinetic Guidelines)

Accrual to Cohort 1 will be temporarily suspended if:

- any participant has a new life threatening event or death judged to be a Suspected Adverse Drug Reaction (SADR) or if any of the participants has a new Grade 4 event that may not be judged to be life-threatening but is judged to be probably or definitely attributable to the study medication;

OR

- at least 4 of the participants have had treatment discontinuation due to non-life threatening Grade 3 or 4 severity SADR, judged to be at least possibly treatment related.

Accrual to Cohort 2 will be temporarily suspended if:

- any participant has a new life threatening event or death judged to be an SADR or if any of the participants has a new Grade 4 event that may not be judged to be life-threatening but is judged to be probably or definitely attributable to the study medication;

OR

- at least 3 of the first 8 participants to be included in the Cohort 2 RAL-unexposed group interim analysis have had treatment discontinuation due to non-life threatening Grade 3 or 4 severity SADR, judged to be at least possibly treatment related;

OR

- if after the Cohort 2 RAL-unexposed group interim analysis,
 - there was no dose adjustment and at least 6 of 20 participants to be included in Cohort 2 final analysis have had treatment discontinuation due to non-life threatening Grade 3 or 4 severity SADR, judged to be at least possibly treatment related; or
 - there was a dose adjustment and at least 4 of the 12 participants on the final dose for Cohort 2 have had treatment discontinuation due to non-life threatening Grade 3 or 4 severity SADR, judged to be at least possibly treatment related.

Following any temporary suspension of accrual, the team will further review the safety data within 48 hours of notification of the event to determine if continuation of accrual is appropriate. If the team, including the study chair, the DAIDS medical officer of record and Merck representatives, agrees that the study drug is likely to be safe for additional participants, they may decide to allow accrual to resume. However, the P1110 SMC will be informed of this decision, and the study will not reopen without the approval of this committee. The SMC may ask for any data it may want to review before making its decision. Regulatory agencies will be notified of the event and the team's and SMC's decision.

8.521 Final Evaluation of Cohort 1 Safety Data

At final evaluation of the Cohort 1 RAL-exposed or RAL-naïve groups, safety guidelines will be assessed on infants on the final dose for each group in Cohort 1 using safety data through week 6 of life. If none of the participants has experienced a new life-threatening event or death judged to be an SADR or a new Grade 4 event that is probably or definitely attributable to the study medication; and no more than 25% of the participants have had treatment discontinuation due to non-life threatening Grade 3 or 4 severity SADR at least possibly related to the study drug, then final dose in Cohort 1 has passed the safety guidelines. Otherwise the team will review the

safety data and will consult with the P1110 SMC to determine whether it is safe to proceed to Cohort 2 and under what conditions this will be allowed to occur.

8.522 Interim Evaluation of Cohort 2 RAL-naïve Group Safety Data

The safety and PK of the starting dose for Cohort 2 will be assessed on the first 8 participants based on safety data through 6 weeks of life, for the purpose of determining whether accrual to the full cohort can proceed and determining if any adjustment in dosing may be necessary (see Section 9.0 for PK evaluation.). Accrual will be stopped while this interim analysis is being performed. Dosing decisions will depend upon severity of adverse events, attribution of these events to the study drug and PK data.

If none of the 8 participants has experienced a new life-threatening event or death judged to be an SADR or a new Grade 4 event that is probably or definitely attributable to the study medication; and no more than 2 of the participants have had treatment discontinuation due to non-life threatening Grade 3 or 4 severity SADR at least possibly treatment related to the study drug, then full accrual to Cohort 2 can proceed. Otherwise the team will review the safety data and will consult with the P1110 SMC to determine whether it is safe to complete full enrollment into Cohort 2 and under what conditions this will be allowed to occur.

8.523 Final Evaluation of Cohort 2 Safety Data

The safety guidelines will be assessed on the final dose for each group in Cohort 2 based on safety data through week 6 of life. If none of the participants has experienced a new life-threatening event or death judged to be an SADR or a new Grade 4 event that is probably or definitely attributable to the study medication and no more than 25% of the participants on the final dose for Cohort 2 have had treatment discontinuation due to non-life threatening Grade 3 or 4 severity SADR at least possibly treatment related to the study drug, then final dose in Cohort 2 has passed the safety guidelines.

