8.53 Probabilities of Failing the Safety Guidelines

The safety guidelines will be assessed at final analysis of Cohort 1, at interim analysis of Cohort 2 and at final analysis of Cohort 2, based on safety data through 6 weeks of life on samples of 12, 8, and maximum of 20 infants, respectively. Given these small sample sizes, the information available for safety decisions will be imperfect. Two types of sampling errors are possible:

- 1) In a group where the true rate of toxicity is too high to warrant increased exposure to the current starting dose of the medication, the sample data may pass the safety guidelines;

- 2) In a group where the true rate of toxicity is low enough that further exposure to the current starting dose is warranted, the sample data may fail the guidelines.

The extent to which the safety guidelines protect against the errors described above can be assessed by examining various hypothetical rates of "true toxicity" which could occur, if the study medication were used extensively among the participant population at the dose level under question. The hypothetical situations presented in Tables 11,12, and 13 are for the sample sizes of the 12 participants in Cohort 1, the first 8 participants for the interim analysis for Cohort 2, and 20 participants for final analysis of Cohort 2, respectively. Should there be a dose change following the interim analysis of Cohort 2, then only the 12 remaining participants will be exposed to the new dose; in that case the probabilities presented in Table 11 will apply. Tables 11,12 and 13 show the probabilities of failing the safety guidelines for a range of conditions under which a given dose level would cause a high incidence of severe and life threatening SADR's to conditions under which severe SADR's would be relatively rare and would not be life threatening. For each of these hypothetical situations, we assume that the sample is drawn from the participant population and that the safety guidelines for Cohort 1 (Section 8.521), interim analysis for Cohort 2 (8.522) and final analysis for Cohort 2 (Section 8.523) are followed.

Table 11.
Probability of Failing Safety Guidelines for a Sample of 12 Participants for Final
Analysis of Cohort 1 Under Potential Rates of True Toxicity

True Toxicity Rates		Probability of Failing Safety Guidelines

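### Section 8.52 has no discontinuation-based accrual-suspension trigger that clearly applies to, or is sized for, the Cohort 2 RAL-exposed group, the only group open under Version 2.0

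*Protocol*

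**What the plan says.** Protocol 8.52 lists four conditions that temporarily suspend accrual to Cohort 2. The first is met by a single event in any infant: a life-threatening or fatal suspected adverse drug reaction (SADR), or a Grade 4 event probably or definitely attributable to raltegravir. The other three count treatment discontinuations for non-life-threatening Grade 3 or 4 SADRs:

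- The interim count is "at least 3 of the first 8 participants to be included in the Cohort 2 RAL-unexposed group interim analysis".
- The first of two later counts, for an unchanged regimen, is worded "there was no dose adjustment and at least 6 of 20 participants to be included in Cohort 2 final analysis have had treatment discontinuation".
- The second, which covers a changed dose, is worded "at least 4 of the 12 participants on the final dose for Cohort 2 have had treatment discontinuation".

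The last two sit under a stem that brings them into force only once the RAL-unexposed interim analysis has taken place. Neither says which exposure group is counted. Section 8.53 evaluates the guidelines "on samples of 12, 8, and maximum of 20 infants, respectively", and says of a dose change after the interim that "then only the 12 remaining participants will be exposed to the new dose".

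Section 8.523, the final evaluation, opens with "The safety guidelines will be assessed on the final dose for each group in Cohort 2" and requires that "no more than 25% of the participants on the final dose for Cohort 2 have had treatment discontinuation".

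Protocol 8.4 states that the other three groups are fully accrued. The RAL-exposed group opens under Version 2.0 with a minimum of 8 infants, expected to take a year. SAP section 2 reports 26 RAL-naïve pairs in Cohort 2, and SAP section 4 says that this group had a single dosing regimen.

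**The concern.** A suspension rule has to tell the team whom to count. Here the only count tied to a group is tied to one that has finished enrolling, and the remaining counts were built for samples of 20 and 12. Following 8.52 as written, 3 of 8 RAL-exposed newborns (37.5%) could stop treatment for SADRs with no obligatory pause. Nor would Study Monitoring Committee (SMC) approval be needed before the next infant is enrolled. Yet the final evaluation, read per group, would fail that dose.

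The scope is narrow. It covers discontinuations for non-life-threatening Grade 3 SADRs and for Grade 4 SADRs judged only possibly related. Anything more serious or more clearly attributable is caught by the single-event condition, which covers every infant.

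**Working it through.** **The plan's own figures.** The thresholds are the smallest counts above 25%, that is floor(0.25n) + 1: 3 for n = 8, 4 for n = 12, 6 for n = 20. With no life-threatening events, the probability of failing is the binomial tail P(X ≥ threshold):

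| n, threshold | rate 5% | rate 25% | rate 50% | protocol table |
|---|---|---|---|---|
| 12, 4 | 0.002 | 0.351 | 0.927 | Table 11: 0.00, 0.35, 0.93 |
| 8, 3 | 0.006 | 0.322 | 0.856 | Table 12: 0.01, 0.32, 0.86 |
| 20, 6 | 0.000 | 0.383 | 0.979 | Table 13: 0.00, 0.38, 0.98 |

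The remaining rows reproduce with a trinomial calculation. So 6-of-20 and 4-of-12 are sized for samples of 20 and 12. In a group of 8, six events is 75%.

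**Which branch is live.** With a single RAL-naïve regimen there appears to have been no dose adjustment, which leaves 6-of-20.

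**Who the 20 could be.**

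1. RAL-naïve infants only. The RAL-exposed group then has no discontinuation trigger.
2. 12 RAL-naïve plus 8 RAL-exposed, which matches the Schema minimums (20 for Cohort 2, 8 of them RAL-exposed). The open group then shares one count with a closed group.
3. All of Cohort 2. The enrolled number would be at least 26 + 8 = 34, not 20. These are enrolled pairs. Section 8.5 drops infants with problematic exposure from the guidelines, and the number left is not given.

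**What a pooled count of six does for 8 RAL-exposed infants.** The rates are hypothetical ones from the protocol's grid. Let X be the number of RAL-exposed discontinuations and r the number already seen in RAL-naïve infants.

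- P(X ≥ 3), the 25% limit exceeded: 0.32 at 25%, 0.86 at 50%.
- P(X ≥ 6), a pooled sixth event when r = 0: 0.004 at 25%, 0.14 at 50%.
- P(X ≥ 3 and X + r < 6), the limit exceeded with no suspension:

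| r | rate 25% | rate 50% |
|---|---|---|
| 0 | 0.32 | 0.71 |
| 1 | 0.29 | 0.49 |
| 2 | 0.21 | 0.22 |
| 3 or more | 0 | 0 |

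The value of r is not given. Protocol 1.29 says the guidelines were met in RAL-naïve infants, but a 25% limit allows up to 5 of 20 or 6 of 26. If the RAL-naïve rate is assumed to be 0 to 10% over 20 to 26 infants, the pooled trigger is reached with probability 0.004 to 0.31 at a RAL-exposed rate of 25%, and 0.14 to 0.69 at 50%.

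**What a pause could achieve.** The expected number of infants enrolled after the third discontinuation is the sum of P(X_t ≥ 3) over t = 3 to 7, where X_t counts events in the first t infants. At 50% this is 0.125 + 0.313 + 0.500 + 0.656 + 0.773 = 2.4. At 25% it is 0.6 and at 5% it is 0.01. These assume instant detection, so for a group of 8 they are upper bounds.

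**The case against.** The strongest reply is that 8.52 and 8.523 do different jobs. One pauses accrual and the other passes or fails a dose, so they need not share a limit. Cohort 1 had the same pairing: its suspension rule was "at least 4 of the participants have had treatment discontinuation", counted over the cohort, while 8.521 judged each group at 25%. That stands. A reader might infer that the two sections flatly contradict each other, and the documents do not support that. On a cohort reading with 20 infants, six is exactly the first count above 25%.

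A reader might also infer that 8.523 is as unclear as 8.52, because its 25% clause mentions Cohort 2. It is not. Its opening words refer to each group, and the mention of Cohort 2 can simply qualify the dose. The RAL-exposed group therefore does have a discontinuation guideline of its own. It operates at final evaluation, however, after enrolment, and cannot pause anything.

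The other safeguards are substantial. Sections 6.11 to 6.13 require team contact and, for Grade 3 or 4 SADRs, notification within 24 hours. Section 7.2 adds expedited reporting. Section 8.51 gives the team responsibility for protective decisions, with calls at least every 4 weeks and SMC review at least annually and ad hoc. At 8 infants a year, about one every 52/8 = 6.5 weeks, a call will on average fall between enrolments. All of this stands, and it lowers the weight. What it does not supply, apart from the single-event condition, is an obligation to pause. The SAP leaves monitoring detail to a Study Monitoring Plan that was not available here.

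**Conclusion.** The point holds as a gap in one rule, of minor to moderate weight. No reading of 6-of-20 gives the only open group a discontinuation trigger that both plainly covers it and fits its size. The third discontinuation in 8 infants, which first exceeds 25%, has probability 0.006, 0.32 and 0.86 at true rates of 5%, 25% and 50%. A pooled sixth event reaches at most 0.004 and 0.14 at the two higher rates if RAL-naïve infants contributed none, and the difference disappears if they contributed three or more.

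A reader might infer that RAL-exposed infants are without safety stopping, or that harm is likely. Neither follows. The single-event trigger covers them, and section 1.29 reports no safety concerns with daily dosing in RAL-naïve infants. The figures are probabilities of a temporary suspension, not of infants spared harm. They rest on 8 infants (a minimum), independent outcomes and hypothetical rates.

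**What to change.** By letter of amendment, reconcile 8.52 with 8.523:

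1. State which infants the 20 comprises.
2. Make the discontinuation-based suspension rule apply to the RAL-exposed group on its own guideline-evaluable infants, consistent with the existing 25% limit. Express it against a planned group size fixed in advance, because 8 is only a minimum and a count that depends on the final number cannot be applied during accrual. The limit is first exceeded at the third discontinuation for a planned size of 8 to 11, and at the fourth for 12.
3. Leave the 48-hour team review and SMC approval unchanged.
4. In SAP 4.7, Table 7, report the guideline endpoints for the RAL-exposed group separately. The present text gives only an overall summary and was written while Version 2.0 was being drafted.

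The cost is a clarified sentence, an added bullet and one table column. The downside is a possible unneeded temporary suspension. For 8 infants its probability is 0.006 at a true 5% rate and 0.32 at 25%, the same risk that Table 12 shows for the RAL-naïve interim. For 11 infants it is 0.015 and 0.54.

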8.53 Probabilities of Failing the Safety Guidelines

The safety guidelines will be assessed at final analysis of Cohort 1, at interim analysis of Cohort 2 and at final analysis of Cohort 2, based on safety data through 6 weeks of life on samples of 12, 8, and maximum of 20 infants, respectively. Given these small sample sizes, the information available for safety decisions will be imperfect. Two types of sampling errors are possible:

- 1) In a group where the true rate of toxicity is too high to warrant increased exposure to the current starting dose of the medication, the sample data may pass the safety guidelines;

- 2) In a group where the true rate of toxicity is low enough that further exposure to the current starting dose is warranted, the sample data may fail the guidelines.

The extent to which the safety guidelines protect against the errors described above can be assessed by examining various hypothetical rates of "true toxicity" which could occur, if the study medication were used extensively among the participant population at the dose level under question. The hypothetical situations presented in Tables 11,12, and 13 are for the sample sizes of the 12 participants in Cohort 1, the first 8 participants for the interim analysis for Cohort 2, and 20 participants for final analysis of Cohort 2, respectively. Should there be a dose change following the interim analysis of Cohort 2, then only the 12 remaining participants will be exposed to the new dose; in that case the probabilities presented in Table 11 will apply. Tables 11,12 and 13 show the probabilities of failing the safety guidelines for a range of conditions under which a given dose level would cause a high incidence of severe and life threatening SADR's to conditions under which severe SADR's would be relatively rare and would not be life threatening. For each of these hypothetical situations, we assume that the sample is drawn from the participant population and that the safety guidelines for Cohort 1 (Section 8.521), interim analysis for Cohort 2 (8.522) and final analysis for Cohort 2 (Section 8.523) are followed.

Table 11.
Probability of Failing Safety Guidelines for a Sample of 12 Participants for Final
Analysis of Cohort 1 Under Potential Rates of True Toxicity

True Toxicity Rates		Probability of Failing Safety Guidelines
Non-life threatening SADR that would result in treatment discontinuation, excluding Grade 4 events probably or definitely attributable to study medication	Death or life- threatening SADR or Grade 4 events probably or definitely attributable to study medication	
0.50	0.00	0.93
0.50	0.05	0.97
0.50	0.25	1.00
0.25	0.00	0.35
0.25	0.05	0.67
0.25	0.25	0.99
0.05	0.00	0.00
0.05	0.05	0.46
0.05	0.25	0.97
0.00	0.05	0.46
0.00	0.25	0.97

Table 12.
Probability of Failing Safety Guidelines for a Sample of 8 Participants for Interim
Analysis of Cohort 2 under Potential Rates of True Toxicity

True Toxicity Rates		
Non-life threatening SADR that would result in treatment discontinuation, excluding Grade 4 events probably or definitely attributable to study medication	Death or life-threatening SADR or Grade 4 events probably or definitely attributable to study medication	Probability of Failing Safety Guidelines
0.50	0.00	0.86
0.50	0.05	0.93
0.50	0.25	1.00
0.25	0.00	0.32
0.25	0.05	0.57
0.25	0.25	0.95
0.05	0.00	0.01
0.05	0.05	0.34
0.05	0.25	0.90
0.00	0.05	0.34
0.00	0.25	0.90

Table 13.
Probability of Failing Safety Guidelines for a Sample of 20 Participants for Final Analysis of Cohort 2 Under Potential Rates of True Toxicity

True Toxicity Rates		
Non-life threatening SADR that would result in treatment discontinuation, excluding Grade 4 events probably or definitely attributable to study medication	Death or life-threatening SADR or Grade 4 events probably or definitely attributable to study medication	Probability of Failing Safety Guidelines
0.50	0.00	0.98
0.50	0.05	1.00
0.50	0.25	1.00
0.25	0.00	0.38
0.25	0.05	0.80
0.25	0.25	1.00
0.05	0.00	0.00
0.05	0.05	0.64
0.05	0.25	1.00
0.00	0.05	0.64
0.00	0.25	1.00

For example, Table 11 shows that for a sample of size 12, there is a 97% chance of failing the safety guidelines under conditions in which the true rate of life-threatening toxicity is 5% and the rate of non-life threatening SADR is 50%. Assuming that it would be undesirable to accrue additional participants at a dose that had these true rates of adverse events, the 3% chance of NOT failing the safety guidelines would represent the probability of error.

